4.10.2 Protocol Deviations

Deviations from the protocol will be documented on an ongoing basis by the study monitors and clinical research associates or designee throughout the study period as detailed in the Protocol Deviation and Non-Compliance Management Plan.

At the time of database lock, prior to unblinding, the project manager or designee will forward all relevant documentation highlighting protocol deviations to the study statistician. These will be listed in the CTR. The study statistician will also verify occurrence of deviations from the protocol checking eCRF data, where feasible.

4.11 Missing Data

The validity of the negative binomial model planned for the primary efficacy analysis of the mean annual CCI [REDACTED] relies on the MAR assumption. CCI [REDACTED] have been outlined in Section 4.7.4.2 of this SAP to investigate the robustness of the primary endpoint conclusion under assumptions of MNAR.

CONFIDENTIAL

Sponsor:	Zambon S.p.A.	Protocol Number:	Z7224L02
----------	---------------	------------------	----------

In the analysis of CCI total score, CCI domain scores and CCI CCI linear mixed models for repeated measures will be used to handle missing data. Under the MAR assumption, these models provide an unbiased estimate of the treatment effect that would have been observed if all subjects had continued on treatment [7].

CCI analyses might be added during the blind review meeting if the amount of missing data makes it reasonable for further investigations of their influence on the overall study results. Decisions will be documented in the Blind Data Review and Analysis Sets Report.

Unless stated otherwise, there will be no imputation of missing values and only observed data will be included in the summaries.

The number of subjects with missing data will be presented under a “Missing” category. Unless otherwise stated, missing values will be included in the denominator count when computing percentages.

When continuous data are being summarised, only the non-missing values will be evaluated for computing summary statistics.

In order to calculate the duration of last usage of colistimethate sodium/colistin and the time from last administration of colistimethate sodium/colistin, the following rules will be applied for partial dates of start and stop date of last administration of colistimethate sodium/colistin:

For the start date:

- if only the day is missing, the first day of the month will be assumed;
- if the day and the month are missing, then the date will not be imputed and the time/duration will be classified as “Not Evaluable”.

For the stop date:

- if only the day is missing, the last day of the month will be assumed;
- if the day and the month are missing, then the date will not be imputed and the time/duration will be classified as “Not Evaluable”.

Where a medication start date is partially or fully missing, and it is unclear as to whether the medication is prior or concomitant, it will be assumed that it is concomitant.

In case of a partial onset date of a NCFB pulmonary exacerbation due to missing day, the onset of the event will be assumed as the first day of the month. If the resultant derived date is prior to the date of first IMP dose, then it will be assumed to be equal to the first IMP dose date.

In case of a partial resolution date of a NCFB pulmonary exacerbation due to missing day, the resolution of the event will be assumed as the last day of the month. If the resultant derived date is after the treatment completion/discontinuation date, then it will be assumed to be equal to the treatment completion/discontinuation date.

In case a NCFB pulmonary exacerbation presents a symptom with missing duration, following a conservative approach, the longest duration will be imputed.

In order to calculate the duration of each course of systemic antibiotic therapy, the following rules will be applied for partial dates of start and stop date of systemic antibiotic therapies:

For the start date:

CONFIDENTIAL

Sponsor:	Zambon S.p.A.	Protocol Number:	Z7224L02
----------	---------------	------------------	----------

- if only the day is missing, the first day of the month will be assumed. If the resulting derived date is prior to the start date of the exacerbation, then start date of therapy will be assumed to be equal to the start date of the exacerbation.
- if the day and the month are missing, then the date will not be imputed.

For the stop date:

- if only the day is missing, the last day of the month will be assumed.
- if the day and the month are missing, then the date will not be imputed and the duration will be classified as “Not Evaluable”.

The domain scores of the CCI will be considered non-missing if the following conditions are satisfied:

- Symptoms score: missing items ≤ 2 ;
- Activity score: missing items ≤ 4 ;
- Impacts score: missing items ≤ 6 .

If at least one domain score is missing, the total score will be considered as missing.

The domain scores of CCI will be considered non-missing if the responses are missing for half or less of the items in the domain.

If an AE has a partially or fully missing date, and it is unclear whether the AE is treatment-emergent, it will be assumed that it is. In the AEs analysis, when relationship to IMP is missing for a TEAE it will be imputed to be drug-related. Every effort should be made to query the site for complete data entry prior to database lock.

Other critical missing data, if any, will be discussed during the blind review of the data. Decisions will be fully documented in the Analysis Set Specifications Document.

4.12 Deviations from the SAP

Any deviations from the original SAP will be described and justified in the final CTR, whether written post interim or final analysis.

4.13 Changes in Conduct or Planned Analyses from the Protocol

Sections 2.2, 4.4.11, 4.7.5 and 4.7.6.3: The protocol incorrectly referred to the units for the determination of CCI CCI which have been reported as CCI by the central laboratory.

Section 4.7.4: The protocol states that the Negative Binomial Model will consider the log-time on study as offset. However, as specified in Section 4.1.7, NCFB Pulmonary Exacerbations analyses focus on the treatment period so log-time on treatment will be considered.

Sections 4.7.5 and 4.7.6.1: The protocol states that the CCI
[REDACTED]
[REDACTED]. Using date of first IMP as the start time of risk is considered to be biased, so date of randomisation will be used instead.

CONFIDENTIAL

Sponsor:	Zambon S.p.A.	Protocol Number:	Z7224L02
----------	---------------	------------------	----------

Section 4.7.6.1: The protocol states that the CCI [REDACTED] CCI [REDACTED] For time-to-event endpoints, generally the + 1 is not included because this overestimates the time by 1 day for every event, therefore “+ 1” has been deleted.

Section 4.7.6.5: The protocol states that the CCI [REDACTED] total score will be computed and analysed. However, as recommended in the Manual Scoring Instructions [REDACTED], only the CCI [REDACTED] domain scores will be presented and analysed.

There have been no other changes in analyses from those defined in the protocol.

CONFIDENTIAL

Sponsor:	Zambon S.p.A.	Protocol Number:	Z7224L02
----------	---------------	------------------	----------

4.14 Algorithms/SAS Codes

The SAS codes for descriptive statistics and frequency counts detailed below are examples only and other procedures may be used, if appropriate.

- **Tables that need descriptive statistics – continuous variables:**

```
PROC UNIVARIATE DATA=dset NOPRINT;
  VAR var1 var2 var3 ...varn;
  BY byvar; (optional)
  OUTPUT OUT= outset
  N=n MEAN=mean MIN=min MAX=max MEDIAN=median STD=std *Q1=q1
  Q3=q3; *Include Q1 and Q3 for CCI data only;
RUN;
```

- **Tables that need frequency counts:**

```
PROC FREQ DATA=dset NOPRINT;
  BY byvar; (optional)
  TABLES var1*var2 /out= outset;
RUN;
```

- **Tables that need T-Test;**

```
PROC TTEST DATA=dset;
  CLASS var1;
  VAR var1N;
RUN;
```

- **Tables that need exact 95% CIs for risk difference between groups for proportions and Fisher's Exact:**

```
PROC FREQ DATA=dset;
  BY byvar; (optional)
  TABLES var*treatment / MEASURES RISKDIFF EXACT ALPHA=0.05;
  EXACT MEASURES;
  OUTPUT OUT= outset EXACT MEASURES RISKDIFF;
  WHERE wherever; (optional)
RUN;
```

- **Tables that need 95% CIs within group for binomial proportions:**

```
PROC FREQ DATA=dset;
  BY byvar; (optional)
  TABLES var1;
  EXACT BINOMIAL;
  OUTPUT OUT= outset BINOMIAL;
RUN;
```

- **Tables that require analysis of (co)variance and 95% CIs between arms for continuous variables:**

```
PROC GLM DATA= dset OUTSTAT=outset;
  CLASS treatment psite med;
```

CONFIDENTIAL

Sponsor:	Zambon S.p.A.	Protocol Number:	Z7224L02
----------	---------------	------------------	----------

MODEL change = treatment psite med baseline/ SOLUTION;
LSMEANS treatment / STDERR PDIFF CL OBSMARGINS;
BY byvar; (optional)
WHERE wherever; (optional)

RUN;

Notes:

- Psite represents the country, as detailed in Section 4.9.1;
- Med represents use of stable concomitant therapy with oral macrolides (e.g. azithromycin or erythromycin or clarithromycin) (Yes/No);
- Change represents the change from baseline of the variable;
- Baseline represents the baseline value of the variable;
- Treatment order: 1= Colistimethate Sodium, 2= Placebo.

• **Tables that require Kaplan-Meier estimates and log-rank test:**

PROC LIFETEST DATA=dset OUTSURV=LIFE METHOD=KM timelist=(0 28 90 180 270 EoT) reduceout;

*TIME time*event (1);*
ID subject;
STRATA treatment;
WHERE wherever; (optional)

RUN;

Notes:

- Time represents the time to event or time to censoring;
- Event represents the censoring indicator (1 = censored);
- EoT should be replaced by the last time (in days) to event >270 days (if any);

• **Tables that require Cox proportional hazards model and 95% CIs of hazard ratios between treatments:**

PROC PHREG data=dset;
CLASS treatment psite med;
*MODEL time*event(1) = treatment psite med / ties=exact;*
HAZARDRATIO 'Col. Sodium vs Placebo' treatment / cl=both;
BY byvar; (optional)
WHERE wherever; (optional)

RUN;

Notes:

- Psite represents the country, as detailed in Section 4.9.1;
- Med represents use of stable concomitant therapy with oral macrolides (e.g. azithromycin or erythromycin or clarithromycin) (Yes/No);
- Time represents the time to event or time to censoring;
- Event represents the censoring indicator (1 = censored);
- If the option ties=exact requires a considerable amount of computer resources, the Efron approximation will be used (*ties=efron*).
- Treatment order: 1= Colistimethate Sodium, 2= Placebo.

CONFIDENTIAL

Sponsor:	Zambon S.p.A.	Protocol Number:	Z7224L02
----------	---------------	------------------	----------

- **Tables that require negative binomial modelling, including 95% CIs of treatment ratios:**

```
PROC GENMOD data = dset;
  CLASS treatment psite med;
  MODEL count = treatment psite med / offset=log_years link=log dist=negbin wald
  type3;
  ESTIMATE 'Col. Sodium / Placebo' treatment 1 -1 / exp;
  lsmeans treatment / ilink cl diff exp om;
  BY byvar; (optional)
  WHERE wherever; (optional)
RUN;
```

Notes:

- Psite represents the country, as detailed in Section 4.9.1;
- Med represents use of stable concomitant therapy with oral macrolides (e.g. azithromycin or erythromycin or clarithromycin) (Yes/No);
- Count represents the total number of exacerbations for each patient;
- log_years represents the logarithm of the follow-up time in years;
- Treatment order: 1= Colistimethate Sodium, 2= Placebo.

- **Tables that require linear mixed model for repeated measures and 95% CIs of differences between treatments:**

```
PROC MIXED data = dset;
  CLASS treatment visit psite med sub;
  MODEL change = treatment visit treatment*visit psite med baseline/ s ddfm=kr;
  REPEATED visit / subject=sub type=un r;
  LSMEANS treatment treatment*visit / om at means cl slice=visit;
  LSMESTIMATE treatment
  'Col. Sodium / Placebo' 1 -1 / cl;
  LSMESTIMATE treatment*visit
  'Col. Sodium / Placebo: Visit 4' 1 0 0 0 -1 0 0 0,
  'Col. Sodium / Placebo: Visit 5' 0 1 0 0 0 -1 0 0,
  'Col. Sodium / Placebo: Visit 6' 0 0 1 0 0 0 -1 0,
  'Col. Sodium / Placebo: Visit 7' 0 0 0 1 0 0 0 -1 / cl;
  BY byvar; (optional)
  WHERE wherever; (optional)
RUN;
```

Notes:

- Visit represents the clinic visit;
- Psite represents the country, as detailed in Section 4.9.1;
- Med represents use of stable concomitant therapy with oral macrolides (e.g. azithromycin or erythromycin or clarithromycin) (Yes/No);
- Sub represents the Subject Number;
- Change represents the change from baseline to each visit of the variable;
- Baseline represents the baseline value of the variable;
- Treatment order: 1= Colistimethate Sodium, 2= Placebo.

CONFIDENTIAL

Sponsor:	Zambon S.p.A.	Protocol Number:	Z7224L02
----------	---------------	------------------	----------

- **Multiple Imputation for pulmonary exacerbation rate**

An example of SAS code is provided below for the **CCI** analyses pulmonary exacerbation rate.

Missing at random and copy reference imputation

```
PROC GENMOD DATA=dataset1act; /* Colistimethate Sodium subjects */
  MODEL count = treatment_d psite_d1-psite_dx med_d / OFFSET=log_years
  DIST=NEGBIN;
  /* >1000 imputations since some will be discarded due to convergence issues with the
  model */
  BAYES NBI=1000 NMC=11000 THIN=10 OUTPOST=dataset2act SEED=34783129;
RUN;
```

```
DATA dataset3act;
  SET dataset2act;
  RENAME treatment_d =c_treatment_d
           psite_d1-psite_dx=c_psite_d1-c_psite_dx
           med_d=c_med_d;
RUN;
```

```
PROC GENMOD DATA=dataset1plb; /* Placebo subjects */
  MODEL count = treatment_d psite_d1-psite_dx med_d / OFFSET=log_years
  DIST=NEGBIN;
  /* >1000 imputations since some will be discarded due to convergence issues with the
  model */
  BAYES NBI=1000 NMC=11000 THIN=10 OUTPOST=dataset2plb SEED=34783129;
RUN;
```

```
DATA dataset3plb;
  SET dataset2plb;
  RENAME treatment_d =c_treatment_d
           psite_d1-psite_dx=c_psite_d1-c_psite_dx
           med_d=c_med_d;
RUN;
```

```
PROC SQL;
  CREATE TABLE dataset4act_mar AS
  SELECT dataset1act.*, dataset3act.*
  FROM dataset1act, dataset3act
  ORDER BY Iteration, Subject;

  CREATE TABLE dataset4act_cr AS
  SELECT dataset1act.*, dataset3plb.*
  FROM dataset1act, dataset3plb
  ORDER BY Iteration, Subject;
```

CONFIDENTIAL

Sponsor:	Zambon S.p.A.	Protocol Number:	Z7224L02
----------	---------------	------------------	----------

```

CREATE TABLE dataset4plb AS
SELECT dataset1plb.*, dataset3plb.*
FROM dataset1plb, dataset3plb
ORDER BY Iteration, Subject;
QUIT;

DATA dataset4all_mar; /* For Missing at Random */
SET dataset4act_mar dataset4plb;
BY Iteration Subject;
RUN;

DATA dataset4all_cr; /* For Copy Reference */
SET dataset4act_cr dataset4plb;
BY Iteration Subject;
RUN;

DATA dataset5_mar; /* Missing at Random */
SET dataset4all_mar;
BY Iteration Subject;
ARRAY c[*] c_psite_d1-c_psite_dx c_med_d;
ARRAY x[*] psite_d1-psite_dx med_d;
k=1/Dispersion;
imp_subj=(years<365/365.25);
years_imp=MAX(years,years_exp);
log_years_imp=LOG(years_imp);
linpred_1=.;
IF imp_subj THEN DO;
years_miss=years_imp-years;
linpred_1=Intercept;
DO i=1 TO DIM(c);
linpred_1+c[i]*x[i];
END;
linpred_mar=linpred_1+c_treatment_d*treatment_d;
y2hat_mar=years_miss*EXP(linpred_mar);
CALL STREAMINIT(3231212);
y2_mar=RAND('NEGBINOMIAL',k/(k+y2hat_mar),k);
y_imp_mar=count+y2_mar;
END;
ELSE DO;
y_imp_mar=count;
END;
RUN;

DATA dataset5_cr; /* Copy Reference */
SET dataset4all_cr;
BY Iteration Subject;
ARRAY c[*] c_psite_d1-c_psite_dx c_med_d;

```

CONFIDENTIAL

Sponsor:	Zambon S.p.A.	Protocol Number:	Z7224L02
----------	---------------	------------------	----------

```

ARRAY x[*] psite_d1-psite_dx med_d;
k=1/Dispersion;
imp_subj=(years<365/365.25);
years_imp=MAX(years,years_exp);
log_years_imp=LOG(years_imp);
linpred_1=.;
IF imp_subj THEN DO;
  years_miss=years_imp-years;
  linpred_1=Intercept;
  DO i=1 TO DIM(c);
    linpred_1+c[i]*x[i];
  END;
  linpred_cr=linpred_1+c_treatment_d;
  y2hat_cr=years_miss*EXP(linpred_cr);
  CALL STREAMINIT(3231212);
  y2_cr=RAND('NEGBINOMIAL',k/(k+y2hat_cr),k);
  y_imp_cr=count+y2_cr;
END;
ELSE DO;
  y_imp_cr=count;
END;
RUN;

```

Notes:

- dataset1 includes one record per patient;
- count represents the total number of **CCI** t;
- treatment represents the treatment group (treatment order: 1 = colistimethate sodium, 2 = placebo);
- treatment_d represent the dummy variables for treatment group (values of the dummy variables: 0 for colistimethate sodium; 1 for placebo);
- Psite represents the country, as detailed in Section 4.9.1;
- psite_d1-psite_dx represent the dummy variables for the country;
- Med represents use of stable concomitant therapy with oral macrolides (e.g. azithromycin or erythromycin or clarithromycin) (Yes/No);
- med_d represents the dummy variable for use of stable concomitant therapy with oral macrolides;
- years represents the observed follow-up time in years;
- years_exp represents the expected follow-up time in years
- log_years represents the logarithm of the follow-up time in years.

Analysis step

The imputed dataset obtained using the above SAS code will be finally analysed and the results will be combined.

```

ODS OUTPUT LSMMeans=lsmmeans_mar Estimates=ratios_mar; /* Missing at Random */
PROC GENMOD DATA=dataset5_mar;
  BY Iteration;

```

CONFIDENTIAL

Sponsor:	Zambon S.p.A.	Protocol Number:	Z7224L02
----------	---------------	------------------	----------

```

CLASS treatment psite med;
/* MAR imputation */
MODEL y_imp_mar = treatment psite med/ OFFSET=log_years_imp DIST=NEGBIN;
LSMEANS treatment / ilink cl diff exp om;
ESTIMATE 'Col. Sodium / Placebo' treatment 1 -1 / exp;
RUN;

DATA lsmeans_mar2;
SET lsmeans_mar (WHERE=(zValue ne .));
BY Iteration;
IF first.Iteration THEN _Imputation_+1;
IF _Imputation_ LE 1000;
RUN;

ODS OUTPUT ParameterEstimates=lsmeans_mar3;
PROC MIANALYZE PARMS=lsmeans_mar2;
CLASS treatment;
MODELEFFECTS treatment;
RUN;

DATA lsmeans_mar4;
SET lsmeans_mar3;
exp_est=EXP(Estimate);
exp_lcl=EXP(LCLMean);
exp_ucl=EXP(UCLMean);
RUN;

DATA ratios_mar2 (RENAME=LBetaEstimate=Estimate);
SET ratios_mar (WHERE=(ChiSq ne .));
BY Iteration;
IF first.Iteration THEN _Imputation_+1;
IF _Imputation_ LE 1000;
Effect='Label';
RUN;

ODS OUTPUT ParameterEstimates=ratios_mar3;
PROC MIANALYZE PARMS =ratios_mar2;
CLASS Label;
MODELEFFECTS Label;
RUN;

DATA ratios_mar4;
SET ratios_mar3;
exp_est=EXP(Estimate);
exp_lcl= EXP (LCLMean);
exp_ucl= EXP (UCLMean);
RUN;

```

CONFIDENTIAL

Sponsor:	Zambon S.p.A.	Protocol Number:	Z7224L02
----------	---------------	------------------	----------

```

ODS OUTPUT LSMeans=lsmeans_cr Estimates=ratios_cr; /* Copy Reference */
PROC GENMOD DATA=dataset5_cr;
  BY Iteration;
  CLASS treatment psite med;
  /* CR imputation */
  MODEL y_imp_cr = treatment psite med/ OFFSET=log_years_imp DIST=NEGBIN;
  LSMEANS treatment / ilink cl diff exp om;
  ESTIMATE 'Col. Sodium / Placebo' treatment 1 -1 / exp;
RUN;

```

```

DATA lsmeans_cr2;
  SET lsmeans_cr (WHERE=(zValue ne .));
  BY Iteration;
  IF first.Iteration THEN _Imputation_+1;
  IF _Imputation_ LE 1000;
RUN;

```

```

ODS OUTPUT ParameterEstimates=lsmeans_cr3;
PROC MIANALYZE PARMS=lsmeans_cr2;
  CLASS treatment;
  MODELEFFECTS treatment;
RUN;

```

```

DATA lsmeans_cr4;
  SET lsmeans_cr3;
  exp_est=EXP(Estimate);
  exp_lcl=EXP(LCLMean);
  exp_ucl=EXP(UCLMean);
RUN;

```

```

DATA ratios_cr2 (RENAME=LBetaEstimate=Estimate);
  SET ratios_cr (WHERE=(ChiSq ne .));
  BY Iteration;
  IF first.Iteration THEN _Imputation_+1;
  IF _Imputation_ LE 1000;
  Effect='Label';
RUN;

```

```

ODS OUTPUT ParameterEstimates=ratios_cr3;
PROC MIANALYZE PARMS =ratios_cr2;
  CLASS Label;
  MODELEFFECTS Label;
RUN;

```

```

DATA ratios_cr4;
  SET ratios_cr3;
  exp_est=EXP(Estimate);
  exp_lcl= EXP (LCLMean);

```

CONFIDENTIAL

Sponsor:	Zambon S.p.A.	Protocol Number:	Z7224L02
----------	---------------	------------------	----------

```
exp_ucl= EXP (UCLMean);
RUN;
```

5 Tables and Listings

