4.1.7 Definition of Exposure Time and Follow-up Time

All the efficacy analyses are focused on the endpoints collected during the treatment period. For these analyses, the exposure time will not include the time from end of treatment to the follow-up call.

The exposure time in days will be calculated using the following formula:

CONFIDENTIAL

Sponsor:	Zambon S.p.A.	Protocol Number:	Z7224L02
----------	---------------	------------------	----------

- Exposure time (days) = [date of treatment completion/discontinuation - date of first IMP dose + 1].

The exposure time in years will be calculated using the following formula:

- Exposure time (years) = Exposure time (days) / 365.25.

Date of treatment completion will be the date of End of Treatment Visit.

Date of treatment discontinuation will be the date of End of Study Visit for subjects who discontinued the study before the End of Treatment Visit. In case a subject is lost to follow-up, the date of treatment discontinuation will be the date of last Study Visit.

Date of last exposure will not include any visits/calls after the end of treatment.

The follow-up time in days will be calculated using the following formula:

- Follow-up time (days) = [date of study completion/discontinuation - date of first IMP dose + 1].

The follow-up time in years will be calculated using the following formula:

- Follow-up time (years) = Follow-up time (days) / 365.25.

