4.7.1 Primary Endpoint

The primary endpoint of this trial is the annual NCFB pulmonary exacerbation rate.

The analysis of this endpoint requires for each subject both their count of NCFB pulmonary exacerbations and their exposure to randomised treatment. NCFB pulmonary exacerbations are defined in Section 4.7.4 and follow-up time is computed as detailed in Section 4.1.7.

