- a worst case approach will be considered for duration of symptoms and requirement of hospitalisation. For example, if one of two exacerbations considered as a single episode has/have increased dyspnoea for ≥ 24 hours and < 48 hours and the other one has increased dyspnoea for ≥ 48 hours, the single episode will be considered in the analysis as having dyspnoea for ≥ 48 hours.

In order to investigate whether the use of inhaled colistimethate sodium reduces the frequency of pulmonary exacerbations compared to placebo in subjects with NCFB chronically infected with *P. aeruginosa*, the following hypothesis will be tested:

- Null hypothesis: there is no difference between inhaled colistimethate sodium and placebo as regards the effect on the pulmonary exacerbation rate
- Alternative hypothesis: inhaled colistimethate sodium reduces the pulmonary exacerbation rate in favour of inhaled colistimethate sodium compared to placebo.

The null hypothesis must be rejected for the efficacy of inhaled colistimethate sodium to be considered demonstrated.

The number and the percentage of subjects with NCFB pulmonary exacerbations, the number of NCFB pulmonary exacerbations and the total follow-up time in years, as defined in Section 4.1.7, will be summarised by treatment group.

The number of NCFB pulmonary exacerbations during the treatment period will be analysed using a negative binomial model including treatment, country, as detailed in Section 4.9.1, and use of stable concomitant therapy with oral macrolides as fixed effects and log-exposure time on treatment as an offset. The log-time on treatment in years will be calculated as $\ln(\text{exposure time})$.

The adjusted mean annual NCFB pulmonary exacerbation rates in each treatment group and the adjusted rate ratio with their 95% CIs will be estimated by the model. OBSMARGINS option will be used for the estimates. The number of subjects considered in the model will be provided by treatment group.

The number and the percentage of subjects with 0, 1, 2 or >2 pulmonary exacerbations will be presented.

The number and the percentage of subjects with pulmonary exacerbations, the number of pulmonary exacerbations will also be presented by treatment group for severe (defined as those requiring intravenous antibiotics and/or hospitalisation) and not severe exacerbations.

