4.9 Adjustment for Covariates

The adjusted mean annual NCFB pulmonary exacerbation rate will be estimated by a negative binomial model including treatment, use of stable concomitant therapy with oral macrolides (e.g. azithromycin or erythromycin or clarithromycin: Yes/No) and country, as detailed in Section 4.9.1, as fixed effects and log-time on treatment as an offset. An exploratory model will also be fitted considering the number of CCI requiring oral/intravenous antibiotics in the last 12 months prior to study entry.

The Cox proportional hazard regression model for CCI will include use of stable concomitant therapy with oral macrolides (e.g. azithromycin or erythromycin or clarithromycin: Yes/No) and country, as covariates.

In the analysis of CCI total score and CCI domain scores, a linear mixed model for repeated measures will be applied. This will include treatment, visit, treatment-by-visit interaction, use of stable concomitant therapy with oral macrolides (e.g. azithromycin or erythromycin or clarithromycin: Yes/No) and country, as fixed effects and baseline value as covariate.

The CCI CCI will be analysed by means of a linear mixed model for repeated measures including treatment, country, and use of stable concomitant therapy with oral macrolides (azithromycin or erythromycin or clarithromycin: Yes/No) as fixed effects and baseline value as covariate.

CONFIDENTIAL

Sponsor:	Zambon S.p.A.	Protocol Number:	Z7224L02
----------	---------------	------------------	----------

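### The SAP 4.14 code notes define the primary model's offset as follow-up time, contradicting the on-treatment offset fixed in SAP 4.7.4, 4.9 and 4.13

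*SAP*

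**What the plan says.** SAP 4.1.7 defines two clocks, both starting at the first dose. Exposure time ends at treatment completion or discontinuation and leaves out the interval to the follow-up call. Follow-up time has its own formula: "Follow-up time (days) = [date of study completion/discontinuation - date of first IMP dose + 1".

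The methods text chooses the first clock for the primary model:
- SAP 4.7.4: "log-exposure time on treatment as an offset", with the logarithm taken of exposure time.
- SAP 4.9: "fixed effects and log-time on treatment as an offset".
- SAP 4.13 declares this as a change from the protocol's time on study: "analyses focus on the treatment period so log-time on treatment will be considered".
- SAP 4.7.6.8 makes a follow-up offset an explicit exception to the primary model.

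SAP 4.1.11 and 4.7.4 limit the counted events to the same window, from first dose to treatment completion or discontinuation.

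Other places use the second term:
- SAP 4.14, note to the negative binomial code: "log_years represents the logarithm of the follow-up time in years".
- SAP 4.14, note to the imputation code: "years represents the observed follow-up time in years", with log_years defined to match.
- SAP 4.7.1 asks for each subject's count and "their exposure to randomised treatment", then states that "follow-up time is computed as detailed in Section 4.1.7". It names no offset.
- SAP 4.7.4 summarises total follow-up time by arm, while its crude annual rate divides events by summed exposure.

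**The concern.** In a rate model the offset has to cover the same period as the count. If events stop counting at treatment completion but the denominator runs on to a later call, the extra days contribute time in which no event can be recorded. The adjusted annual rates are a stated output of the primary analysis, and the primary endpoint is itself named as a rate, so their denominator should not depend on which section the programmer reads. Two programmers working independently from the methods text and from the code notes could report different rates. The person-years displayed under 4.7.4 would also not reproduce the crude rate. In the imputation, the same variable decides who is imputed and for how long.

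**Working it through.** **Inputs from the documents.** The call is 2 weeks ± 3 days after treatment stops (Protocol 9.6), so the gap is d = 14 days (11 to 17). Treatment lasts 12 months, taken as 365 days. The placebo rate is 1.09 a year and the effect 35% (Protocol Summary, Sample Size), so the active rate is 1.09 × 0.65 = 0.7085. Visit 7 has a window of ± 1 week (Protocol 9.5).

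**Assumptions.** The date of study completion is the date of the call for completers, and withdrawn subjects gain no added time. The SAP states neither.

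**Plan's own figures.** The plan gives no number that depends on this choice. Its power statement supplies only a plausible dispersion k. With variance (1/1.09 + 1/m1 + 2k)/170, where m1 is the active rate, k = 0.25 gives 91.6% and 80.4% power for effects of 35% and 30%, and k = 0.30 gives 90.7% and 79.0%, against the stated 90% and 80%. The means and variances are redacted, so k is solved for and the power is not independently reproduced.

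**Annual rate, full-term completer.** The rate is multiplied by 365/(365 + d).

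| d (days) | Denominator (days) | Understatement | 1.09 becomes |
|---|---|---|---|
| 11 | 376 | 11/376 = 2.9% | 1.058 |
| 14 | 379 | 14/379 = 3.7% | 1.050 |
| 17 | 382 | 17/382 = 4.5% | 1.042 |

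At d = 14 the active rate of 0.7085 becomes 0.682. If subjects with curtailed treatment also had the call time added, the understatement would be 14/284 = 4.9% at 270 days of exposure and 14/194 = 7.2% at 180 days.

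**Rate ratio.** Let completers have 365 days plus 14, and withdrawals 180 days plus none (assumed).
- Equal completion: the factors cancel and 0.65 stays 0.65.
- Completion 90% active, 70% placebo: active 346.5/(346.5 + 12.6) = 0.9649; placebo 309.5/(309.5 + 9.8) = 0.9693; factor 0.9955; 0.65 becomes 0.647.
- The reverse: factor 1.0046; 0.65 becomes 0.653.

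**Simulation.** Each of three scenarios used 300 trials with 144 subjects per arm, k = 0.337 and no covariates, each trial fitted with both offsets.

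| Completion, active/placebo | Rate ratio, exposure v follow-up | Power, exposure v follow-up |
|---|---|---|
| 80% / 80% | 0.654 v 0.654 | 0.820 v 0.820 |
| 90% / 70% | 0.658 v 0.655 | 0.807 v 0.810 |
| 70% / 90% | 0.661 v 0.664 | 0.787 v 0.773 |

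At 80% completion the placebo rate was 1.091 against 1.055. The largest power difference is 4 trials in 300, and a few fits returned no standard error.

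**Imputation.** The code flags a subject when years is below 365/365.25 and sets the offset to the larger of observed and expected time. Take a completer whose expected duration is 365 days and whose Visit 7 falls a week early, at 358 days. With exposure time, 7 days are imputed, about 1.09 × 7/365.25 = 0.02 events at the placebo rate. With follow-up time the value is 358 + 14 = 372 days, so nothing is imputed and the offset passes the 365-day cap on expected duration in 4.7.4.2. Exposure time can also pass the cap when Visit 7 is late. With follow-up time, every such completer seen within the window would pass it, since the shortest value is 358 + 11 = 369 days.

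**The case against.** The strongest reply is that the methods text settles the matter. Three sections and one explicit exception all point to time on treatment, so the code note is a leftover label. The SAP is also loose with the term: 4.7.6.1 equates last follow-up with treatment completion or discontinuation, 4.7.6.6 places later days outside the follow-up period, and 4.7.4.2 compares expected exposure with realised follow-up as if they were one clock. On that usage the notes have no numerical effect. The negative binomial code is a shared template that also serves the 4.7.6.8 model, where a follow-up offset is intended, and the imputation program is introduced as an example.

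Much of this stands. The intended offset is clear, the inclusion of the call is an inference, and follow-up time should not be removed from 4.14 altogether. Two parts do not stand. The sentence in 4.14 that limits code to examples covers descriptive statistics and frequency counts, not the negative binomial model. And 4.1.7 gives follow-up time a formal definition that differs from exposure, so a literal reader of the notes is led to the wrong denominator.

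A reader might also infer that anyone who stops up to two weeks early would pass as complete in the imputation. The documents do not support that. For subjects who leave the study early, 4.1.7 ends exposure at the End of Study Visit, where study discontinuation would apparently also fall. What remains is the completer with an early Visit 7, a shortfall of at most about 7 days.

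**Conclusion.** Wrong as written, with minor impact. The 4.14 notes contradict the offset fixed elsewhere in the SAP. If followed literally, they would lower adjusted annual rates by about 3.7% for full-term completers (2.9% to 4.5%). This assumes that study completion means the follow-up call. It is not an estimate for the whole trial, because recruitment was stopped and many subjects may not have had a full year of treatment.

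Two stronger readings are tempting and do not hold. One is that the treatment effect is at risk: the rate ratio is unchanged with equal completion and moves by under 0.5% in the direct calculation (about 0.5% in simulation) with a 20-point completion gap. The other is that 4.7.1 prescribes a follow-up offset: it uses both terms and names no offset, so it is ambiguous rather than contrary.

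**What to change.** - In SAP 4.14, define log_years for the primary and severe-exacerbation rate models, and years and log_years in the imputation code, as exposure time per 4.1.7.
- Change follow-up time to exposure time in 4.7.1 and in the person-time summary of 4.7.4, so that the displayed person-years reproduce the crude rate.
- Keep follow-up time as the offset only for the 4.7.6.8 model, and give that model its own note, because it shares the code template.
- Define the date of study completion in 4.1.7, stating whether it is the date of the call.

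The cost is SAP wording and code comments. No data collection or design change is involved.
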